13 PRECLINICAL AND CLINICAL EXPERIENCE

HAMS is a prebiotic that is a well-tolerated source of dietary fiber with selective fermentation properties. In T1D mouse studies [21], feeding HAMS that has been acetylated and butyrylated (HAMSA and HAMSB) shifts the gut microbiome profile towards fermenters, resulting in increased acetate and butyrate production and lower rates of progression to T1D, Figure 1.

In a human study assessing the effects of 2 levels of intake of HAMS [15 or 30 g/d (double-blind)] compared to control starch intake (0 HAMS) for 4-wk periods separated by 3-wk washouts on insulin sensitivity (SI) in participants with increased waist circumference, it appeared that the consumption of 15–30 g/d of HAMS improved insulin sensitivity significantly in men, Figure 2 [27].

In another human randomized, double-blind, controlled study [28] in healthy adults who consumed either a high fiber scone containing a novel chemically modified high amylose maize starch or a low fiber control scone without the maize starch, the consumption of the high fiber scone significantly reduced postprandial glucose and insulin incremental areas under the curves (43–45% reduction, 35–40% reduction, respectively) and postprandial glucose and insulin maximum concentrations (8–10% and 22% reduction, respectively), Figure 3. Of note, ingestion of the high fiber scone consumption was not associated with increased gastrointestinal side effects compared with the control scone.

Figure1: Incidence of T1D in female NOD mice fed the NP diet ($n = 25$ mice), HAMS diet ($n = 17$ mice), HAMSA diet ($n = 11$ mice), HAMSB diet ($n = 12$ mice) or combined (HAMSA plus HAMSB) diet ($n = 11$ mice) for 10 weeks (HAMSA plus HAMSB; orange arrows) or 5 weeks (all other diets; blue arrows), starting at 5 weeks of age. NS (NP vs HAMS, HAMSB vs HAMS, HAMSP vs HAMS, and HAMSP vs NP); $*P = 0.0482$ (HAMSB vs NP), $\#P = 0.0490$ (HAMSA vs HAMS), $**P = 0.0069$ (HAMSA vs NP), $\#\#P = 0.0025$ (HAMSA+HAMSB vs HAMS) and $***P = 0.0008$ (HAMSA+HAMSB vs NP) (Mantel-Cox log-rank test) [22].

Conventional, non-purified (NP), High-amylose maize starch (HAMS) that has been acetylated (HAMSA) or butyrylated (HAMSB), non-significant (NS).

[figure not shown]

Figure 2: Insulin sensitivity (SI) following 4-wk feeding periods for control (0 g/d HAMS), 15 g/d HAMS, and 30 g/d HAMS in men ($n = 11$) and women ($n = 22$). Bars represent least squares geometric means and error bars extend to the value of the \log_e least squares mean \pm 1 SEM, back transformed to the original units. Labeled means without a common letter differ, $P < 0.05$. Least squares mean and SEM values for \log_e SI were generated from repeated-measures ANOVA models containing terms for participant as a random variable, treatment condition, treatment sequence, and measures of insulin sensitivity [27].

[figure not shown]

Figure 3: Mean post-prandial glucose and insulin concentrations over 180 min after ingestion of a scone containing a chemically modified maize resistant starch: a. venous glucose, b. capillary glucose, c. venous insulin. Error bars represent the standard error of the mean [28].

14 SCIENTIFIC RATIONALE

To date, there have been no studies assessing the effect of using a prebiotic, such as HAMS-AB, on the gut microbiome profile, glycemia and β -cell function in humans with T1D. In addition, there are no data linking changes in the gut microbiome and their metabolites in response to administration of HAMS-AB to metabolic changes in youths with T1D. This study will examine repurposing an existing, safe supplemental product for the treatment of T1D.

2.0 - OBJECTIVES

2.1 Primary Objective

Assess the effect of administering HAMS-AB on the gut microbiome profile in people with recently diagnosed T1D.

2.2 Secondary Objectives

Assess the effect of administering HAMS-AB on SCFA production in people with recently diagnosed T1D.

[figure not shown]
Determine the effect of HAMS-AB on glycemia and β -cell function and health.

3.0 - STUDY DESIGN

3.1 STUDY DESCRIPTION

This study will be a single center, controlled, randomized trial in young individuals newly diagnosed with type 1 diabetes. We are enrolling youth with new onset T1D with documented continued residual C-peptide production. Within 30 days of screening during which eligibility will be determined, subjects will have a 4-week treatment period with HAMS-AB or will be provided with guidelines on the generally recommended diabetic diet for youths with T1D [49, 50]. After a 4-week wash-out period the durability of effect will be assessed in those who received the prebiotic and during this washout period, both the study and control arm will be permitted to consume a regular diet. This design has been used in other studies of prebiotic administration with a 3–4-week intervention period and a 3–4-week washout phase [21, 32, 33]. Subjects will then cross over to either HAMS-AB or diet control for another 4 weeks.

A full dosing description can be found in section 6.2.

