6.1 STUDY DESIGN

6.2 RANDOM ASSIGNMENT

Subjects will be randomly assigned (6 in each arm) to either HAMS-AB plus a recommended diabetic diet or control diabetic diet alone [49, 50] for the first 4 week of treatment period. After a suitable washout period during which participants do not need to follow the recommended diet or use the supplement, subjects will continue for 4 weeks after a cross-over. All participants will be expected to follow the guidelines for a healthy diabetic diet during the study period, except for during the 4-week washout period.

A computer-based randomization plan will be prepared by the principal investigator. The document will be kept by the study team for use. As a subject is screened and qualifies, he/she will be assigned in order of screening date on the computer-generated document. One master list will be maintained in a confidential central shared folder for use. Subjects will be replaced on an ongoing list if they drop out.

Participants will be instructed to consume HAMS-AB with food, such as apple sauce or oatmeal, in two divided doses at breakfast and dinner at a total daily dose to be calculated as has been previously described for children: 10g plus 1g per year of age daily [44]. The prebiotic will be dispensed by the Investigational Drug Services (IDS) at Indiana University.

HAMS-AB will be in the form of acetylated and butyrylated **HYLON® VII** corn starch.

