- Measurement of weight, assessment of CGM insertion sites, as well as bedside nurse assessment such as general appearance, respiratory and cardiac assessment.
- Obtaining vital signs (heart rate, temperature, blood pressure, and respiratory rate)
- Collecting a diet history (diary or questionnaire)
- Collecting Adverse Events (if applicable)
- Obtaining medical history and insulin use
- Obtaining blood samples (approximately 2tablespoon) – Serum biomarkers of beta cell stress and death (PI:C and INS DNA), other T1D testing, and serum and plasma for storage
 - Some of the blood will be stored for future T1D research use
- For female adolescents: urine will be collected for a pregnancytest
- Supplement (HAMS-AB) will be provided and will be taken by mouth twice daily in the treatment arm as above in addition to insulin for diabetes management. Those in the control arm will follow standard diabetes management in addition to a recommended diabetic diet.
- New CGM supplies given, if applicable.
- Collecting stool samples 3 days prior to or the morning of the visit
- A new stool collection kit will be provided for the next visit

Visit 5 Follow-Up and/or Early Termination Visit

This visit will be at the hospital or research center, will last approximately 2-4 hours and will include:

- Measurement of height and weight and assessment of CGM insertion sites
- Obtaining vital signs (heart rate, temperature, blood pressure, and respiratory rate)
- Collecting a diet history (diary or questionnaire)
- Collecting Adverse Events (if applicable)

- Obtaining medical history and insulin use
- Obtaining blood samples (approximately 5 tablespoons) – HbA1c, Serum biomarkers of beta cell stress and death (PI:C and INS DNA), MMTT samples (see above), other T1D testing, and serum and plasma for storage
 - Some of the blood will be stored for future use
- For female adolescents: urine will be collected for a pregnancy test
- Completion of a mixed meal tolerance test(MMTT) See Visit 3 for details.
- CGM download
- Collecting stool samples prior to or the morning of the visit

An early discontinuation MMTT will only be done if it has been at least 6 weeks since the last MMTT.

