8.0 STATISTICAL CONSIDERATIONS

A sample size of 12 with a cross over design (i.e., 12 per arm) is considered adequate to estimate effect sizes for efficacy to aid in designing future trials for responses that are normally distributed [52]. Simple comparisons will be performed using chi-square for categorical variables and t-tests for continuous variables. Random attritions and failed screens will be replaced. An intention to treat analysis will not be appropriate given the crossover design. Adverse events will be presented as the proportion of each event seen. This is considered a minimal risk study with low risk for minor adverse events such as mild gastrointestinal symptoms that could be related to increased dietary fiber intake. Our primary outcome is changes in the gut microbiome profile. To determine the diversity and richness of the microbiome, we will calculate a diversity index for both the pre- and post-intervention time points for each recipient. Microbial sequence analysis and statistics will be analyzed using the Quantitative Insights into Microbial Ecology (QIIME) 1.8.0 software as previously described [53].

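### Durability of the HAMS-AB effect is described among recipients with no comparator, although the control-first arm already supplies the samples for a controlled between-sequence estimate

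*Combined protocol and SAP*

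**What the plan says.** Section 3.1 of the combined protocol and SAP sets out the assessment: "After a 4-week wash-out period the durability of effect will be assessed in those who received the prebiotic". It adds that "during this washout period, both the study and control arm will be permitted to consume a regular diet".

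Section 6.2 gives the allocation: "Subjects will be randomly assigned (6 in each arm) to either HAMS-AB plus a recommended diabetic diet or control diabetic diet alone". It also confirms when the diet applies: "All participants will be expected to follow the guidelines for a healthy diabetic diet during the study period, except for during the 4-week washout period". In section 6.4, the instruction to eat normally and take no supplement is given once, at the end of Visit 3.

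Visit 4 closes the washout. Its procedures include, for every participant, "Collecting stool samples 3 days prior to or the morning of the visit", and blood for PI:C and INS DNA. HbA1c, the MMTT and a CGM download are not among them.

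The section on statistical considerations names chi-square tests, t-tests and a diversity index before and after intervention. It gives no durability contrast and no comparison of the sequences at Visit 4.

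**The concern.** The schedule has no visit after Visit 5, so participants who take HAMS-AB second are never observed off it. Durability can be seen only in the HAMS-AB-first sequence. In that sequence, withdrawal of the supplement coincides with lifting of the diet.

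Read literally, the plan would look at those six participants alone. A shift that fades could reflect the diet stopping, and a shift that lasts could reflect time or a leftover diet effect. The pilot is meant to inform a fully powered study, for which persistence of effect bears on the length of washout and on whether a crossover is suitable. An uncontrolled estimate would be a poor guide to either.

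**Working it through.** **Plan's own figure.** The sample size is 12, and 6 + 6 = 12 agrees with the allocation. No SD, effect size, alpha or power is given, so there is nothing further to reproduce.

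**What is scheduled** (sections 6.3 and 6.4):

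| Outcome | Visit 2 | Visit 3 | Visit 4 | Visit 5 |
|---|---|---|---|---|
| Stool | yes | yes | yes | yes |
| PI:C, INS DNA | yes | yes | yes | yes |
| Dietary assessment | yes | yes | yes | yes |
| HbA1c | yes | no | no | yes |
| MMTT C-peptide | no | yes | no | yes |
| CGM download | no | yes | no | yes |

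SCFA has no row of its own in the schedule. I assume it is measured on the same stool samples.

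**What each contrast contains.** Let h3 and h4 be the HAMS-AB effect at Visit 3 and what remains of it at Visit 4. Let d3 and d4 be the diet effect at those visits, and t3 and t4 the change due to time since Visit 2.

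- HAMS-AB first, Visit 3 minus Visit 2: h3 + d3 + t3
- HAMS-AB first, Visit 4 minus Visit 2: h4 + d4 + t4
- HAMS-AB first, Visit 4 minus Visit 3: (h4 − h3) + (d4 − d3) + (t4 − t3)
- Control first, Visit 3 minus Visit 2: d3 + t3
- Control first, Visit 4 minus Visit 2: d4 + t4

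Subtracting control-first from HAMS-AB-first leaves h3 at Visit 3 and h4 at Visit 4, provided that d and t are the same in both sequences.

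**Size of the diet term.** If the diet effect has gone by Visit 4 (d4 = 0), the within-recipient Visit 3 to Visit 4 change carries −d3 in full. A diet shift of 0.3 to 0.5 SD (an assumption; the documents give none) then gives a bias of 0.3 to 0.5 SD. The Visit 2 to Visit 4 change carries only d4 + t4. Visit 2 precedes the study diet and Visit 4 follows four weeks without it, so d4 may be small.

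**Precision**, in SD of the change score, with equal SDs in the two sequences:

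- Six recipients alone: t(0.975, 5)/√6 = 2.571/2.449 = 1.05
- Six versus six: t(0.975, 10) × √(2/6) = 2.228 × 0.577 = 1.29
- Ratio: 1.286/1.049 = 1.23

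**Error rates.** These come from 40,000 simulated trials with normal changes from Visit 2 to Visit 4, SD 1 and two-sided alpha 0.05. The shared shift d4 + t4 is assumed. True persistence is zero.

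| Shared shift | Within six: mean estimate | Within six: false positives | 6 v 6: mean estimate | 6 v 6: false positives |
|---|---|---|---|---|
| 0 | 0 | 4.9% | 0 | 4.8% |
| 0.5 SD | 0.50 | 17.3% | 0 | 5.2% |
| 1 SD | 1.00 | 50.5% | 0 | 5.1% |

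With true persistence of 0.5 SD, the 6 v 6 contrast has about 12% power. It needs about 1.80 SD for 80% power.

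**The case against.** The strongest reply is that durability is peripheral. It is absent from the primary and secondary objectives, from the endpoints and from the statistical section, and appears in one clause of the design description. The endpoints section already expects too little power for glycemic and MMTT outcomes, and nowhere does the plan promise durability results for HbA1c, CGM or C-peptide in particular. Diet is recorded at Visits 2 to 5, so a change in intake would be visible. Section 3.1 does not exclude the control arm, and Aim 2 foresees comparing intervention and control groups on glycemic and β-cell measures. All of this stands and keeps the point minor. It does not supply the missing contrast: Aim 2 does not mention Visit 4, and recording diet does not remove its effect.

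A reader might infer three stronger things that the documents do not support:

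- **Persistence cannot be separated from diet and time at all.** This is true only of a within-recipient analysis. The control-first arm is randomised, changes diet at the same point and is sampled at the same visits.
- **The diet effect biases any durability estimate in full.** That applies to Visit 3 to Visit 4. Visits 2 and 4 are both off the study diet, so only a residual diet effect enters that change.
- **Incomplete washout would shrink the crossover estimate by a known amount.** The plan does not say whether periods are compared on end values or on changes from period start. A residual effect that persists shrinks the first. One that decays during period 2 inflates the second, and one that stays constant leaves the second unbiased. Neither sign nor size can be stated.

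**Conclusion.** The point holds as a gap in the stated analysis. Durability has no comparator or contrast, and a within-recipient reading is confounded with diet and time at Visit 3 to Visit 4, and with time and residual diet at Visit 2 to Visit 4. For the microbiome, PI:C and INS DNA, the scheduled data can resolve this. For HbA1c, CGM and MMTT C-peptide they cannot, because nothing is scheduled at the end of washout. Some participants' own CGM devices may hold washout readings, but no Visit 4 download is planned.

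The size of any bias is unknown; the shifts used in the working are illustrations. The controlled contrast assumes similar diet and time changes in both sequences, which an open-label design does not guarantee. With a half-width of about 1.29 SD it is an estimate for planning. A null Visit 4 difference would not be evidence that washout was complete. This is a minor but real improvement.

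**What to change.** In section 3.1 and in the statistical considerations:

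1. Define durability as the between-sequence difference in change from Visit 2, using all 12 participants, with a 95% CI. Report it at Visit 3 (effect at the end of period 1) and at Visit 4 (what remains). Both are needed: a null at Visit 4 alone cannot tell an effect that faded from one that never occurred.
2. Apply it to the stool microbiome, PI:C and INS DNA, and to SCFA if that is measured on the same stool samples.
3. State that no durability conclusion will be drawn for HbA1c, CGM or MMTT C-peptide.
4. State the assumption of similar diet and time changes in the two open-label arms, and that a null Visit 4 difference at 6 v 6 does not establish complete washout.

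The cost is wording and analysis only, with no new visits or samples. The price is a confidence interval about 23% wider than the uncontrolled one and a narrower durability claim.

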32 STUDY DURATION

This study will screen up to 24 subjects at a single center (see Enrollment below). 12 subjects will be enrolled after meeting all eligibility criteria. If at any time during the study, a participant does not meet eligibility, participation in the study will be on hold until subject meets all eligibility criteria again. Participants may re-enter or re-enroll in the study if in the future, meet all eligibility requirements. Participants who re-enter or re-enroll will need to be reassessed for their starting point. Subjects who miss 20% of prebiotic doses (11 of 56 doses) will be replaced. The study will include the following periods:

- (1) Screening visit and eligibility determination (up to 30 days).
- (2) 4-week intervention period or diet guideline
- (3) 4-week washout period
- (4) 4-week intervention period or diet guideline.

33 ENROLLMENT

Up to 24 subjects will be screened to find 12 adequate subjects eligible for enrollment.

The plan is to recruit 24 patients with the goal of having 50% eligible and enrolled. Once 12 participants have completed the 12 week visit, we will stop recruitment. At Indiana University, as per our current recruitment strategies for other new-onset studies, patients with newly diagnosed T1D will be approached whenever possible when inpatient at diagnosis and then re-contacted after discharged home. Visits will be conducted at the Indiana Clinical Research Center (ICRC) and coordinated with diabetes clinic follow-up visits when possible.

34 STUDY ENDPOINTS

The primary outcome assessment will be to assess changes in the gut microbiome profile in response to HAMS-AB. Secondary outcome measures will be changes in SCFA production, changes in glycemia, pro-insulin to C-peptide ratios as a marker of β cell ER stress. Other β cell stress markers including unmethylated insulin DNA will also be measured. We will also examine glycemic outcomes and β cell function as assessed by responses to MMTT, although given the variability in these measures in other reported studies of new-onset T1D [43] we do not expect to be adequately powered in this small trial to see significant differences in these outcomes.

35 STUDY RISKS

Risks include those risks related to taking HAMS-AB, having blood draws, mixed meal tolerance tests (MMTT), risk of CGM use, and the possible loss of confidentiality.

Risks of Taking HAMS-AB:

Given that most youths in the United States are consuming less than the recommended dietary intake of fiber, we anticipate the following risks:

- Likely (reported in >20% of patients): initial abdominal discomfort, increase in frequency of bowel movements, although not to the extent of causing diarrhea. These mild intestinal symptoms will likely last for only the first few days and are self-limited without intervention.

Risk of Blood Draws:

The insertion of a needle can cause some local pain and can result in bruising. Blood draws can in rare instances cause lightheadedness or fainting. There is also a risk of infection. To mitigate these risks, blood draws will be performed by trained technicians or nurses using standard aseptic techniques.

Risk of MMTT:

There are no known risks to an MMTT, but the taste of the Boost may not be well tolerated. Some persons may experience nausea after drinking Boost. Subjects with milk or soy allergies will be excluded to avoid any allergic

reactions to Boost. If the blood glucose is high at the end of the test, subjects will be instructed to give an insulin correction dose.

Risks related to CGM use:

The CGM/sensor may produce pain when it is inserted into the skin. There is a low risk for developing a local skin infection at the site of the sensor needle placement. Itchiness, redness, bleeding, and bruising at the insertion site may occur as well as local tape allergies.

Loss of Confidentiality:

There is the unlikely chance that health information is viewed by someone outside of the research team who is not authorized to see health information. All files will be kept in locked cabinets within a locked room. Any electronic data will be protected by password systems.

